15.2 Statistical methods

The modified intention-to-treat analysis of efficacy outcomes and safety outcomes were performed on the full analysis set, which was composed of all patients who received randomization independent of treatment and at least 1 efficacy evaluation after enrollment. The χ^2 test was used in the unadjusted analysis. A modified Poisson regression model with robust error estimation was used to analyze the primary outcome and other dichotomous endpoints, with adjustment for prespecified covariates (age, male and onset-to-needle time). Relative risk (RR) with a 95% confidence interval (CI) was calculated in both unadjusted and adjusted analyses. Generalized linear models (GLMs) were used to analyze continuous endpoints, including NIHSS scores, Barthel scale scores, and hematoma and edema volumes. The distribution of mRS was analyzed using an ordinal logistic regression model, and odds ratios (OR) with 95% CI were calculated. Post hoc subgroup analysis was performed for the primary outcome according to age, sex, and baseline NIHSS scores, with an OR of 95% CI. No interim analyses were performed.

A 2-sided P value <.05 is considered statistical significance. Because multiple comparisons potentially cause type I error, findings for secondary outcome analyses should be interpreted as exploratory. SPSS software (version 26, IBM) and R software (version 4.1.0) are used for the statistical analyses.

16. Data Management

The enrolled participants were entered in the case report form (CRF) by the evaluator within 24 hours and entered in the electronic form within 3 days. All of the entered personnel signed on the CRF. The assessors were blinded to allocation information. A data supervisor who was not involved in clinical research is set up for data verification. Two investigators who blinded to allocation information rechecked the original data, and if the data was found to be wrong, the data should be corrected in time. The data of modification and the person who modified it should be recorded to ensure that the data is correct.

17. Data and Security Monitoring Board (DSMB)

A Data and Security Monitoring Board (DSMB) was established in this study in order to ensure the integrity of the trial and protect the rights and health of subjects. During the study period, regular monitoring visits will be made to the clinical site to ensure that all procedures were complied with the approved protocol/amendment. The safety and efficacy of the interventions were assessed at interim time-point and DSMB had the authority to terminate the trial.

18. Ethical Considerations

The study protocol was approved by the Institutional Ethics Committee (EC) of the Affiliated Hospital of Jiujiang University (Jiujiang, China, 2020001) in accordance with the guidelines of the 1964 Declaration of Helsinki. All participants or their legally authorized representative provided written informed consent.

Modify the protocol: The research agreement must be strictly followed. The revised research agreement must be approved by the ethics committee, and the revised research agreement can be implemented after approval.

Protocol adherence: Prior to beginning the study, the Investigator must sign the Investigator Agreement and Signature page documenting his/her agreement to conduct the study in accordance with the protocol. An Investigator must not make any changes or deviate from this protocol, except to protect the life and physical well-being of a subject in an emergency. Each deviation from the protocol must be documented with the date and reason for the deviation and reported to EC as soon as possible.

Written informed consent form: The informed consent Form (ICF) document should be translated into a language that the subject can understand. The informed consent must be approved by the ethics committee before use. ICF must agree with the current Good Clinical Practice (GCP) guidelines and the Declaration of Helsinki. Before participating in a clinical trial, each subject or its legally authorized representative (LAR) must understand the content of the informed consent form and sign it. The informed consent should clearly indicate the rights and obligations of the subjects. The written informed consent must be properly recorded with the signature of the person or LAR. The consent process must be recorded in the subject's medical record.

References

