7.1 Trial plan

This is a single-center, prospective, assessor-blinded, randomized, controlled, two-arm (1:1 ratio) clinical trial registered at Clinicaltrials.gov (http://www.clinicaltrials.gov; unique identifier: NCT04144868) and has been approved by the Institutional Ethics Committee (Affiliated Hospital of Jiujiang University).

All patients within 24 hours from definite onset time are screened by the cranial computed tomography (CT) to confirm ICH at admission. And then the patients sign the consent and are allocated to two arms: the NBO group and the control group. In the NBO group, patients receive high-flow oxygen via oxygen storage face mask (100% O₂, flow rate 8 L/min, 1 hour, four times daily, and 2 L/min via nasal catheter during intermittent periods, for 7 days) immediately in the emergency room after randomization. In the control group, patients receive 2 L/min flow of 100% O₂ via nasal catheter in the emergency room after randomization, for 24 hours daily for 7 days. Meanwhile, the participants undergo routine medication treatment, including dehydration treatment, antihypertensive therapy and sedative treatment, and if necessary, hematoma aspiration or a decompressive craniectomy will be conducted.

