7.4 Randomization and blinding

All patients are enrolled consecutively and randomized in 1:1 ratio to receive 8 L/min flow of 100% O_2 via oxygen storage face mask or 2 L/min flow of 100% O_2 via nasal catheter using a computer-generated randomization code. This is an open label trial, so we adopt a partial blinding strategy where the clinical assessors are blinded to the treatment allocation but the operators are not. That is, the neurological functional scores and imaging tests are assessed by investigators blinded to the

intervention and grouping. The operators responsible for oxygen interventions to the patients are unblinded.

	STUDY PROTOCOL					
	Enrollment	Allocation		Foll	ow-up	
TIMEPOINT	0 day	0 day	3 days	7 days	14 days	90 days
ENROLLMENT						
Eligibility screen	Х					
Informed consent	Х					
Allocation		Х				
INTERVENTIONS						
NBO		←		\longrightarrow		
Control		←		\longrightarrow		
ASSESSMENTS						
Personal data		Х				
Safety evaluation				Х		
NIHSS	Х		Х	Х	Х	
Glasgow Coma Scale	х		Х	Х	Х	
Barthel index						Х
mRS						Х
Cranial CT	Х		Х	Х	Х	
CT perfusion	Х			Х		

8. Trial Flow Chart

NBO, normobaric hyperoxia; CT, computed tomography; NIHSS, National Institute of Health Stroke Scale; mRS, modified Rankin Scale.

9. Interventions

All patients within 24 hours from definite onset time are screened by the cranial CT to confirm ICH at admission. After diagnosis of ICH, the patient or his certigiers will decide whether to participate in this

trial. If they agree, an informed consent will be signed, and allocation will proceed.

Participants will be allocated into two arms:

The NBO group, undergoing high-flow oxygen via oxygen storage face masks (100% O₂, flow rate 8 L/min, 1 hour, four times daily, and 2 L/min via nasal catheter during intermittent periods, for 7 days) immediately in the emergency room after randomization.

The control group, undergoing 2 L/min flow of 100% O₂ via nasal catheter in the emergency room after randomization, for 24 hours daily for 7 days.

Secondary stroke prevention follows the 2022 AHA/ASA guidelines for the diagnosis and treatment of acute intracerebral hemorrhage. All participants are hospitalized for at least 14 days, and if the hematoma expands and causes cerebral hernia, hematoma aspiration or a decompressive craniectomy will be conducted.

10. Measurements

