10.1 Imaging test

10.1.1 Non-contrast cranial CT image

Non-contrast head CT scans are performed to assess the severity of hematoma and perihematomal edema (PHE). A 256-slice CT scanner is used following standard local protocols. Next, 5-mm-thick CT images are measured for hematoma and PHE volumes using the General Electric Company workstation built-in image software. All volume measurements are performed using a semi-automated process involving tracking the perimeter of appropriately high- and low-attenuation areas and calculating the lesion area for each slice multiplied by the slice thickness to obtain the lesion volume. Independent analysis of all images is performed by two doctors blinded to the treatment assignment, and any discrepancies are resolved consensually.

Cranial CT scans are performed at admission, day 3, 7, and 14. Software from United Imaging (United Imaging Healthcare Co., Ltd., Shanghai, China) is used for the automated calculation of hematoma and absolute PHE volumes. The relative PHE is calculated by dividing the absolute PHE volume by the baseline hematoma volume to obtain a dimensionless ratio. The reduction volumes of the hematoma, absolute PHE, and relative PHE follow the defined formula: baseline volume – follow-up volume. Besides, the clearance rate of the hematoma, absolute PHE and relative PHE are calculated as a percentage using the defined formula: $100\% \times (baseline volume - follow-up)$

volume)/baseline volume.

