10.2.3 National Institute of Health Stroke Scale (NIHSS)

The NIHSS is commonly used to evaluate neurological deficits in stroke and comprises five items in 11 fields of different neurological statuses (scores range from 0–42, representing normal to severe neurological deficits). The NIHSS is scored at admission, 3-day, 7-day and 14-day after randomization during hospitalization.

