11.2 Safety outcomes

The 7-day oxygen pressure (PO₂), the 7-day carbon dioxide pressure (PCO₂) and the 7-day PH value, as well as the death rate and the complication rate (including hematoma expansion, pulmonary infections, acid-base imbalances and so forth) during hospitalization.

12. Study Flow Diagram

13. Study Periods

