13.2 In-hospital periods

The patients who are assigned to the NBO group receive 100% O₂ via oxygen storage face masks (flow rate 8 L/min, 1 hour, four times daily, and 2 L/min via nasal catheter during intermittent periods, for 7 days), otherwise, the patients receive 2 L/min flow of 100% O₂ via nasal catheter for 24 hours daily for 7 days. Secondary stroke prevention follows the 2015 AHA/ASA guidelines for the diagnosis and treatment of acute intracerebral hemorrhage.⁶ Blood samples are collected at 7 days. Cranial CT is performed at 3 days, 7 days and 14 days, and cranial CTP is performed at 7 days after randomization. NIHSS score and GCS score are assessed at 7 days and 14 days after randomization.

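### Safety is analysed on a set that requires an efficacy evaluation, so a treated patient with an early death, or an early complication followed by loss to follow-up, can fall outside the safety rates

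*Combined protocol and SAP*

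**What the plan says.** Section 15.2 assigns both kinds of outcome to a single population: "The modified intention-to-treat analysis of efficacy outcomes and safety outcomes were performed on the full analysis set". That set is "composed of all patients who received randomization independent of treatment and at least 1 efficacy evaluation after enrollment". Membership therefore has two conditions: being randomized, and having one or more efficacy assessments afterwards. No other section defines a safety population.

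The safety outcomes in section 11.2 are day-7 blood gas and pH values, "as well as the death rate and the complication rate", the last two counted over the hospital stay. The named complications include hematoma expansion, pulmonary infection and acid-base imbalance.

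On timing, section 7.1 has the NBO arm start oxygen "immediately in the emergency room after randomization". For the assessments, section 10.1.1 says "Cranial CT scans are performed at admission, day 3, 7, and 14" and section 10.2.3 says "The NIHSS is scored at admission, 3-day, 7-day and 14-day after randomization during hospitalization". Section 10.2.4 gives the same days for the GCS.

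**The concern.** A safety analysis should count everyone exposed, from the first exposure. Here a patient enters the safety denominator only after producing an efficacy measurement, and the schedule leaves an interval between the start of oxygen and the first such measurement. The patients most likely to have no measurement are those who die or leave the trial soonest, and their events are the ones a safety analysis most needs. When such a patient is left out, the event and the person disappear from the rate together.

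Safety is one of the two aims stated in section 6, and the trial closed with 48 patients per arm (section 15.1). At that size a single event is visible in the reported percentage.

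**Working it through.** The plan gives no figure that depends on this definition, so there is nothing to reproduce. The check sets the set definition against the schedule, and then illustrates the size.

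**Step 1: is there an exposed interval?**

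| Item | Timing | Section |
|---|---|---|
| Oxygen starts | Day 0, after randomization | 7.1, 9 |
| First visit after baseline | Day 3 | 7.3 |
| First post-baseline CT | Day 3 | 10.1.1, 13.2 |
| First post-baseline NIHSS and GCS | Day 3 | 10.2.3, 10.2.4 |
| mRS and Barthel index | Day 90 | 10.2.1, 10.2.2, 13.3 |

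Section 13.2 lists the NIHSS and GCS at days 7 and 14 only, but still has "Cranial CT is performed at 3 days, 7 days and 14 days". Day 3 is therefore the first scheduled efficacy evaluation on either account. From day 0 to day 3 a patient is treated and has no scheduled evaluation that would satisfy section 15.2.

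**Step 2: who could be left out?**

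- *A patient who dies before day 3 with no unscheduled CT or score.* Read literally, this patient fails the second membership condition. The only route back is to treat the death itself as an evaluation, through mRS category 6 (section 10.2.1). No text says that this qualifies.
- *A living patient with an early complication who then leaves follow-up.* Section 7.2.3 lists acute respiratory disease, acid-base imbalance, other severe complications and refusal of further follow-up as withdrawal criteria. It does not say whether assessments continue after withdrawal. If none is made, the patient fails the condition, and mRS 6 does not apply.

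**Step 3: size, by assumption.** The documents report no deaths and no exclusions, so every event count here is assumed. Take an arm of n = 48 with d deaths, one of them before any evaluation.

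- All treated patients: d/48.
- Current rule, read literally: (d − 1)/47.
- Difference: d/48 − (d − 1)/47 = (48 − d)/(48 × 47) = (48 − d)/2256.

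| d (assumed) | All treated | Current rule | Difference |
|---|---|---|---|
| 1 | 1/48 = 2.1% | 0/47 = 0% | 47/2256 = 2.1 points |
| 2 | 2/48 = 4.2% | 1/47 = 2.1% | 46/2256 = 2.0 points |
| 4 | 4/48 = 8.3% | 3/47 = 6.4% | 44/2256 = 2.0 points |

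Each excluded early death lowers that arm's rate by about two percentage points. The same arithmetic applies to a complication rate. With no exclusions the difference is zero.

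**The case against.** The best defence is that a known death already has a determined efficacy result. Section 10.2.1 makes death mRS 6, and section 11.1.1 places 4 to 6 in the poor-outcome group. Section 15.2 neither defines an efficacy evaluation nor ties it to a scheduled visit. If the assigned 6 counts, the patient is in the full analysis set, and because one set serves both purposes, in the death rate too. This is a reasonable reading and may be what the investigators did. But the mRS is scheduled for day 90 and no sentence says that an assigned score qualifies. The reading also does nothing for a living patient who has an early complication and then leaves.

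Other points narrow the concern, and they stand:

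- The interval is short. Eligibility (section 7.2) requires GCS above 8 and a hematoma of 10 to 30 mL, and excludes life-threatening conditions, so very early death is less likely.
- Section 9 says "All participants are hospitalized for at least 14 days", so an early in-hospital death would be known.
- A CT or score taken before day 3 outside the schedule would admit the patient. A hematoma expansion measured on such a scan supplies its own qualifying evaluation.
- Fatal events are SAEs under section 14.2 whatever the analysis set. The open question is who is counted in the rates, not whether deaths are recorded.

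A reader might go further and infer that early deaths were dropped, that a harm of NBO is hidden, or that the primary result depends on this rule. The documents support none of these. They report no deaths or exclusions, and any imbalance between arms would have to be invented. For the primary outcome, the mRS scoring of death points towards keeping such a patient.

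**Conclusion.** The point holds as a flaw in the definition of the safety population. The rule is explicit: safety outcomes depend on having an efficacy evaluation, there is an interval of treatment before the first scheduled one, and no safety set overrides it. Applied literally, it can omit an early death, or an early complication in a patient who leaves follow-up.

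The severity is minor. Whether anyone was affected is unknown, and so is the direction of any difference between arms. The figure of about two percentage points per excluded death assumes 48 patients in the arm, one exclusion and the invented death counts shown. It is not an estimate of what happened. The conclusion also assumes that an assigned mRS of 6 is not counted as an evaluation; if it is, the death rate is protected and only the early-complication case remains.

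**What to change.** Three changes to section 15.2 and the report:

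1. Define a safety set of all randomized patients who received any study oxygen, with no efficacy-evaluation condition, and analyse deaths, complications and the other safety outcomes on it.
2. State that a death before day 90 is scored mRS 6 and that this score qualifies the patient for the full analysis set.
3. Report, by arm, how many patients the current rule excluded and why. If the answer is none, one sentence closes the point.

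The cost is a wording change and a small re-analysis of data already recorded, since deaths are captured as SAEs. How to handle living patients without a 90-day mRS is a separate missing-data question that these changes do not settle.

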15.1 Sample size calculation

The sample size was estimated according to previous trials, with an expected between-group difference of 18 percentage points in favorable outcomes (90-day mRS 0-3, 81% in the NBO group, and 61% in the control group). We set the effective size to 0.25, α error probability to 0.05, power (1- β error probability) to 0.8, and the loss rate to 10%, the final result is that the total sample size is 154. However, the interim analysis showed the profound efficacy of NBO on ICH patients demonstrated by both imaging presentations and clinical evaluations. So, we terminated the trial ahead of schedule, and enrolled 96 participants (NBO group, 48 cases, and control group, 48 cases) at last.

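### Section 15.2 has no zero-cell rule for rare safety events: if one arm of 48 has none, robust Poisson gives a risk ratio of 0 or infinity with a spuriously tiny P value

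*Combined protocol and SAP*

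**What the plan says.** Section 15.2 puts efficacy and safety in one analysis: "The modified intention-to-treat analysis of efficacy outcomes and safety outcomes were performed on the full analysis set". For binary endpoints it then specifies: "A modified Poisson regression model with robust error estimation was used to analyze the primary outcome and other dichotomous endpoints". The same sentence sets three covariates for that model: age, sex and the onset-to-needle interval. Next to this it plans a simpler comparison: "The χ^2 test was used in the unadjusted analysis". An RR with a 95% CI is promised for both the adjusted and the unadjusted analysis. The threshold is: "A 2-sided P value <.05 is considered statistical significance".

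Section 11.2 lists, besides blood-gas values, "the death rate and the complication rate (including hematoma expansion, pulmonary infections, acid-base imbalances and so forth) during hospitalization". Section 15.1 gives the final size: "enrolled 96 participants (NBO group, 48 cases, and control group, 48 cases").

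Nowhere does the plan give an exact test, a penalised model, a minimum event count or a rule for an arm with no events. It gives no expected rate for death or for any complication.

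**The concern.** None of the secondary outcomes in 11.1.2 is dichotomous: they are the mRS distribution, scale scores, volumes and perfusion values. The general phrase about other dichotomous endpoints in 15.2 therefore has only the safety outcomes of 11.2 to refer to.

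Robust Poisson is a sound choice for a common outcome such as 90-day mRS 0-3. It fails when one arm is empty. The log RR has no finite estimate, so the software stops at a large arbitrary value, and the sandwich variance does not reflect this. The output is a very small P value and a meaningless interval. If the NBO arm is the empty one, this looks like protection; if the control arm is empty, it looks like harm. Safety is one of the two things the objectives in section 6 set out to examine, so one or two events could be read as a highly significant difference.

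**Working it through.** The plan has no figure of its own to reproduce here, because it states no safety event rate or precision.

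**Inputs.** 48 patients per arm (15.1), all assumed to be in the full analysis set; two-sided .05, Poisson with robust errors, three covariates and an unadjusted chi-square test (15.2). True event rates of 2% to 10%, equal in both arms, are assumed.

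**Standard error with one empty arm.** In the two-group model, the robust variance of the log mean in an arm is Σ(y − μ)² / (nμ)².
- Arm with a events (μ = a/n): the variance is (1 − a/n)/a.
- Empty arm: every y is 0 and the fit stops at some small μ > 0. The variance is nμ²/(nμ)² = 1/n, whatever that μ is.
- For 0/48 v 3/48: SE = √(1/48 + (45/48)/3) = √(0.0208 + 0.3125) = 0.577.
- In general 1/n + (1 − a/n)/a = 1/a, so SE = 1/√a: 1.00, 0.71, 0.58 and 0.50 for a = 1 to 4.

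Fitted in statsmodels, the unadjusted log RR stops near −20 to −21:

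| Events | Robust Poisson P | Chi-square P | Fisher P |
|---|---|---|---|
| 0 v 1 | 2e-92 | 0.315 | 1.00 |
| 0 v 2 | 9e-183 | 0.153 | 0.49 |
| 0 v 3 | 2e-300 | 0.078 | 0.24 |
| 0 v 4 | about 0 | 0.041 | 0.117 |

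Adding three covariates gave P = 8e-5 for 0 v 1 in one data set, 5e-92 for 0 v 2 and 5e-293 for 0 v 3. For 0 v 2 and 0 v 3, the model-based (non-robust) SE exceeds 10,000 with P = 1.0, so the false precision comes from the robust variance. In R 4.3.3 (the plan names 4.1.0), fits for 0 v 1 to 4 all reported convergence; no unadjusted fit and only two of four adjusted fits gave a warning. SPSS was not tested.

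**How often it happens.** With q = (1 − p)^48, the chance that exactly one arm is empty is 2q(1 − q). At 2%, q = 0.379 and 2 × 0.379 × 0.621 = 0.471. At 5%, q = 0.085 and 2 × 0.085 × 0.915 = 0.156. Rejection rates with no true difference come from exact enumeration over both binomials. The adjusted model was simulated with 1,000 or 2,500 runs per rate; where two runs were made, both results are shown.

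| True rate | One arm empty | Poisson, unadjusted | Poisson, adjusted | Chi-square | Fisher |
|---|---|---|---|---|---|
| 2% | 47% | 47% | 45%, 48% | 1.2% | <0.1% |
| 3% | 36% | 36% | 36% | 2.8% | 0.2% |
| 4% | 24% | 24% | 24%, 24% | 4.2% | 0.4% |
| 5% | 16% | 16% | 15% | 5.2% | 0.7% |
| 6% | 10% | 10% | 11% | 5.8% | 0.9% |
| 8% | 3.6% | 4.6% | 5% | 6.1% | 1.4% |
| 10% | 1.3% | 3.1% | 4%, 3% | 5.9% | 1.7% |

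At low rates almost all of the excess comes from samples with one empty arm. When both arms have events, the unadjusted model rejects no more than the nominal 5% at the rates tried (0.5% to 30%).

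**The case against.** **A false signal cannot be called likely.** A reader might infer that a spurious safety finding is likely in this trial. The documents do not support that: they give no safety event rates. For one endpoint the chance of exactly one empty arm cannot exceed 50%, since 2q(1 − q) peaks there, and from about 8% upward the model is not materially inflated. The entry criteria in 7.2 and the in-hospital window for death make low counts plausible, but that is not an estimate. This objection stands, and the point is conditional on rare events.

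**The complication rate may be one composite.** Section 11.2 can be read that way, and a composite is less likely to leave an arm empty than a single component. This stands as a limit on scope. Death remains a separate endpoint, and any component tested alone is exposed.

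**The planned chi-square test is a check.** For 0 v 1 to 3 it gives P above .05 and visibly contradicts the adjusted result. At rates of 1% to 10%, chi-square and unadjusted Poisson reject together in at most 3.9% of trials. This mitigates the problem but does not cure it, because 15.2 does not say which result governs, and at 0 v 4 chi-square (.041) no longer contradicts the Poisson result.

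**The chi-square test might seem equally unsound.** Expected counts are below 5 per arm for fewer than 10 events in total, so a reader might dismiss it too. Its exact rejection rate never goes above about 6% in the table, so no material harm follows.

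**Findings are labelled exploratory.** That caveat in 15.2 names secondary outcomes; 11.2 lists safety separately.

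**Conclusion.** The concern holds in conditional form. If a safety event has a true rate of about 5% or less and exactly one arm of 48 has no events, the model in 15.2 gives an RR of 0 or infinity and a P value that cannot be used. With no true difference, it rejects in about 47% of trials at a 2% rate, 24% at 4%, 16% at 5% and 10% at 6%. At 8% and 10% the unadjusted model rejects in under 5%, and the adjusted simulation agrees to within its error. These figures rest on assumed event rates, 48 analysed per arm, and each endpoint tested on its own.

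A reader might also infer that the trial's safety results are wrong, or that modified Poisson should be barred from all safety endpoints. The documents support neither: they report no safety counts, and the model behaves acceptably for commoner events.

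This is a should-fix. The primary outcome, with assumed rates of 81% and 61%, has no sparse cells. No decision rule in the plan depends on a safety P value, and 15.1 gives efficacy as the reason for stopping early.

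**What to change.** Add to 15.2: for death and any complication with zero or very few events in either arm, the governing analysis is an unadjusted exact test (Fisher or mid-P) with a risk difference and a score-type 95% CI (Newcombe or Miettinen-Nurminen), and no robust-Poisson P value or RR is reported. State very few as a number. The calculation here shows the failure only for zero events, so any higher cut-off is a judgement to be stated. Choose one test and one interval and name them. Keep modified Poisson for the 90-day mRS outcome and for commoner complications.

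The interval also conveys what the data leave open. For 0/48 v 3/48, Newcombe gives −16.8 to +2.2 percentage points, and 0/48 alone is compatible with a true rate up to 1 − 0.025^(1/48) = 7.4%.

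Cost: a few sentences of text, no covariate-adjusted RR for rare safety events, and re-analysis of any affected result, since 15.1 and 15.2 describe enrolment and analysis largely in the past tense.

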7.2 Eligibility criteria

7.2.1 Inclusion criteria:

 supratentorial hematomas confirmed by admitted cranial CT, with the volume ranging from 10 to 30 mL; (2) age 18-80 years;

(3) National Institute of Health Stroke Scale (NIHSS) ≥ 6 and Glasgow Coma Scale (GCS) > 8 at admission;

- (4) onset-to-enrollment time ≤ 24 h;
- (5) signed informed consent.

7.2.2 Exclusion criteria:

(1) a history of ICH, ischemic attack, brain tumor, brain trauma, and other intracranial injury or disorders;

- (2) pre-stroke modified ranking scales (mRS) \geq 1;
- (3) life-threatening condition;
- (4) pre-stroke complicated with austere diseases such as cancer, heart failure, and respiratory failures;
- (5) severe liver and kidney disorders;
- (6) a history of respiratory diseases;
- (7) poor compliance;
- (8) participation in other clinical trials within the previous three months.

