13.1 Screening periods

Within 24 hours of symptom onset, participants who are diagnosed as ICH are assigned to either the NBO group or control group. The demographic features, medical history, onset-to-needle time, cranial CT imaging, blood pressure, blood samples and neurological measurements (NIHSS score, mRS score and GCS score) are collected.

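### The adjusted primary model omits baseline NIHSS and hematoma volume, and the GLMs as written omit the endpoint's own baseline: a possible loss of precision, not a bias

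*Combined protocol and SAP*

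**What the plan says.** Section 15.2 gives an unadjusted chi-square test and a modified Poisson model with robust errors for the primary outcome, "with adjustment for prespecified covariates (age, male and onset-to-needle time". For continuous outcomes it says "Generalized linear models (GLMs) were used to analyze continuous endpoints, including NIHSS scores, Barthel scale scores, and hematoma and edema volumes", and for the ordinal outcome "The distribution of mRS was analyzed using an ordinal logistic regression model, and odds ratios (OR) with 95% CI were calculated". Neither sentence names a covariate. Baseline NIHSS enters the analysis only here: "Post hoc subgroup analysis was performed for the primary outcome according to age, sex, and baseline NIHSS scores". Secondary analyses carry the caution that "findings for secondary outcome analyses should be interpreted as exploratory".

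The omitted values exist. The flow chart (section 8) and sections 10.1.1, 10.1.2, 10.2.3 and 10.2.4 schedule cranial CT, CT perfusion, NIHSS and GCS at admission. Section 7.2.1 uses NIHSS and hematoma volume for entry, the latter "with the volume ranging from 10 to 30 mL". Section 7.4 describes 1:1 allocation "using a computer-generated randomization code" and mentions no stratification.

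**The concern.** Severity is balanced neither by stated stratification nor by the adjusted primary model, in a trial that closed at 96 patients against 154 planned. If baseline NIHSS and hematoma volume predict 90-day mRS in this sample, including them would narrow the interval around the relative risk at almost no cost. For NIHSS, GCS, CT volumes and perfusion, the endpoint's own admission value is an obvious candidate covariate, and the GLM sentence does not include it. What is at stake is the width of intervals and the credibility of an estimate from a small trial. The validity of the randomized comparison is not in question.

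**Working it through.** **Plan's own figure.** The documents give no precision or power for the adjusted model, so there is none to reproduce.

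**Inputs from the documents.** 48 per arm; 81% v 61% (15.1); two-sided 0.05 (15.2). Section 15.1 also states an 18-point difference, although 81 − 61 = 20.

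**Unadjusted power at 48 per arm.**
- 81% v 61%: null SE = √(2 × 0.71 × 0.29/48) = 0.0926; alternative SE = √((0.81 × 0.19 + 0.61 × 0.39)/48) = 0.0903; z = (0.20 − 1.96 × 0.0926)/0.0903 = 0.20; power 58.1%.
- 79% v 61% (one reading of 18 points): z = (0.18 − 1.96 × 0.0935)/0.0917 = −0.04; power 48.5%.

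**Primary model, by simulation.** 8,000 trials per setting, logistic outcome with those marginal rates, HC1 robust variance in both models. Assumed, because the documents are silent: NIHSS and volume standardized, correlated 0.4, equally weighted; age effect 0, 0.4 or 0.8 log-odds per SD; sex (60%) and time without effect. The stated model has treatment, age, sex and time. The expanded model adds NIHSS and volume. Power ranges run over the three age effects; SE of log RR is the median at age effect 0.4. Changes were taken before rounding, with Monte Carlo error of 0.2 to 0.5 points.

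| Combined severity effect (log-odds per SD) | Power, stated | Power, expanded | Change, points | SE, stated to expanded | CI width |
|---|---|---|---|---|---|
| 0 | 54.8–58.7% | 53.8–57.1% | −1.6 to −0.6 | 0.1373 to 0.1392 | +1.4% |
| 0.3 | 54.2–58.8% | 53.6–58.0% | −0.7 to −0.4 | not tabulated | not tabulated |
| 0.5 | 54.8–58.4% | 55.8–58.4% | 0.0 to +1.0 | 0.1373 to 0.1369 | −0.3% |
| 0.8 | 55.5–58.9% | 58.4–60.9% | +1.9 to +2.9 | 0.1371 to 0.1338 | −2.4% |
| 1.1 | 55.7–57.8% | 60.8–62.2% | +4.4 to +5.2 | 0.1378 to 0.1312 | −4.8% |
| 1.5 | 55.3–56.9% | 63.7–64.3% | +7.4 to +8.8 | 0.1379 to 0.1280 | −7.2% |
| 2.0 | 54.8–56.0% | 66.5–67.1% | +11.1 to +11.7 | 0.1384 to 0.1243 | −10.2% |

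Break-even lies between 0.3 and 0.5. Under the null (71% in both arms) rejection was 4.1–4.7% for the stated model and 4.1–4.6% for the expanded one.

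**Different assumptions.** Two independent covariates, uncorrected sandwich variance in both models, 3,000 trials per setting. An odds ratio per SD of 1.0 for each gave 58.8% to 58.2%; 2.0 gave 56.4% to 61.0%; 3.0 gave 55.9% to 67.5%. The pattern is the same.

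**Variance estimator.** HC1 multiplies the variance by n/(n − k). The SE factor is √(96/91) = 1.027 in the stated model (k = 5 with intercept) and √(96/89) = 1.039 in the expanded one (k = 7). Setting an uncorrected stated model beside an HC1 expanded model can therefore cancel a modest gain: at 0.8 a run gave 59.6% v 59.3%, against 57.1% v 59.3% with HC1 in both.

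**GLMs.** With correlation r between baseline and follow-up:
- Adjusted v follow-up only: variance ratio 1 − r², a cut of 9%, 25% or 64% at r = 0.3, 0.5 or 0.8.
- Reduction volumes already subtract baseline. With equal variances the ratio is (1 − r²)/(2(1 − r)) = (1 + r)/2, a cut of 35%, 25% or 10%.

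No figure is claimed for clearance rates, the Barthel index or the ordinal mRS model.

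**Model size.** Expected poor outcomes: 96 × 0.29 = 27.8. Per coefficient: 27.8/4 = 7.0 stated, 27.8/6 = 4.6 expanded.

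**The case against.** The plan names its covariates, calls them prespecified, and reports an unadjusted result beside them. A short list is defensible with about 28 expected poor outcomes. The gain rests entirely on assumed prognostic strength. The upper end of the range, 2.0 log-odds per SD, is an odds ratio of about 7.4, in a population narrowed to 10–30 mL, NIHSS of at least 6 and GCS above 8. Enrollment is closed, so the lost power cannot be recovered, and a model added now is post hoc.

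Most of this stands. It limits the primary-model part to a supportive analysis and rules out quoting any single gain. It does not remove the point: the values are already collected, the added model costs little, and readers of a small trial with no stated stratification will ask whether the estimate survives adjustment for severity.

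Two further objections stand as limits. Power of 55–59% holds only for 81% v 61%, and the 18-point reading lowers it throughout. It is also a fixed-sample figure, whereas 15.1 says the trial stopped on interim results. A reader might blame the covariate list for the low power, but that comes from the 96 enrolled. Nor is it shown that the GLMs were fitted without the own baseline: the sentence is silent, so the GLM figures apply only if it was left out.

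**Conclusion.** The point holds as a possible loss of precision. In the primary model the change is nil or slightly negative below roughly 0.3 to 0.5 log-odds per SD. It is about 2 to 3 power points at 0.8 and 11 to 12 at 2.0, given 48 per arm, 81% v 61% and the same variance estimator in both models. In the GLMs the gain is r squared against a follow-up-only model, for exploratory endpoints.

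A reader might infer that the primary result is biased or invalid without severity adjustment. The documents do not support that: allocation is randomized, and leaving out baseline covariates does not bias the marginal relative risk. A reader might also take the subgroup use of baseline NIHSS as evidence that it is strongly prognostic here; the documents give no such estimate.

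The missing definition of onset-to-needle time (collected under 13.1, used in 15.2) and the unlisted covariates of the ordinal mRS model are reporting notes only.

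**What to change.** 1. In 15.2, include the endpoint's own admission value in the GLMs for NIHSS, GCS, hematoma and PHE volumes, and the perfusion parameters. If it was already included, say so. If it is added now, label it as added after the interim look. Cost: one coefficient per model.
2. Keep the stated adjusted primary model as the reported one. Beside it, report a modified Poisson model that adds baseline NIHSS and baseline hematoma volume, both continuous, with the same robust variance estimator in both models; name that estimator. Label the added model a supportive analysis specified after the interim look reported in 15.1. It cannot replace the stated model.
3. As reporting notes, define the start and end of onset-to-needle time as recorded, and list the covariates of the ordinal mRS model.

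The cost is added text, one further primary-model run and, where needed, refitted GLMs, all on scheduled data. The downside is about 4.6 instead of 7.0 expected poor outcomes per coefficient, and a CI about 1.4% wider if neither baseline is prognostic.
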